Effect of High Rebound Mattress Toppers on Sleep and Sleep-Related Symptoms

Statistical Analysis Plan

NCT03055156

October 13, 2020

SPSS Statistics for Macintosh, version 26 (IBM corp, Armonk, NY) was used for all analysis.

To compare topper effects on sleep [TST, SE, SL, WASO, % of stages of Wake, REM, N1, N2, N3 out of TST], sleep related-factors [Position change frequencies, AHI, and heart rate], and VAS, independent sample t-tests were used.

Topper effects on Core body temperature (CBT) was analyzed using two-way mixed method ANOVA with time and topper type as effects. Topper effects on Mean EEG delta spectral power per second over 90 mins was analyzed using independent sample t tests for each 90 min time bin from lights off (i.e. 0-90min, 90-180 min, 180-270 min, 270-360min).

Significance levels for all analysis were set to $p=0.05$.

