The study will be conducted over a 4-year period to compare the effects of airweave® with Tempur-Pedic® mattress toppers on top of regular mattress (equipped in the Stanford Sleep Disorders Clinic) on sleep and core body temperature. Currently, several different types of mattresses are equipped at the clinic, and we first plan to standardize the mattresses in all rooms at the clinic in order to avoid any confounding factor for the evaluation. Sleep will be evaluated using polysomnography (PSG) using metrics to evaluate sleep (e.g. sleep latency, wake after sleep onset (WASO), sleep efficiency, and delta wave EEG power) and sleep-related symptoms (e.g. apnea hypopnea index, periodic leg movements and position changes).

In healthy volunteers, the major effect of airweave® was a drop in core body temperature (monitored using a rectal probe) shortly after sleep onset (1,2). Additional weaker effects on sleep quality (i.e., increase in deep slow wave sleep and change in EEG delta power) that were expected based on the larger drop in temperature were also observed (1,2). At the sleep clinic, measuring rectal temperature using a rectal temperature probe would be difficult, since we plan to recruit from “patients that visit the clinic”. We therefore propose to monitor core body temperature using VitalSense, an ingestible capsule telemetry from Philips/Respironics (4). The telemetry compares in size to a large gel capsule and will be swallowed with liquid. The ingestible VitalSense temperature capsule easily travels and passes through the gastrointestinal tract without affecting other bodily functions and will wirelessly send temperature data continuously to the receiver placed in the recording room. Patient will have the option to use the capsule as a suppository if they prefer.

We will analyze sleep and sleep related symptoms in segments (e.g. hourly or every 2-hours) as

well as continuously over the entire night, since the major effects on the core body temperature are seen during the initial phase of sleep (1,2). Finally, we will collect subjective data on how well patients slept, which is standard clinic protocol after a sleep study.

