To use a patient population will dramatically reduce cost and will allow us to study a large number of subjects. The pilot study was performed in healthy volunteers and as a cross-over design, whereas the proposed study will use a parallel randomized design in a larger sample. We expect that the majority of patients that participate in the study will have sleep apnea (or suspected sleep apnea), but at the end of the study, we will also have a considerable patient population that suffer from insomnia, restless legs syndrome and hypersomnia with various origins. A patient's symptoms and diagnosis will be recorded using the Alliance Sleep Questionnaire (5), a comprehensive, branching logic questionnaire that is used as standard of care at the clinic to evaluate severity and types of sleep problem. Doctor based diagnosis will be also extracted from EPIC (our Electronic Medical Record System). Based on this information, we will systemically analyze effects that are seen in specific diseases or patients with specific characteristics.

Year 1:

As mentioned above, preliminary data used a cross over design and a rectal probe in a small number of healthy subjects. This is an ideal design, but would be very costly to perform at the sleep clinic. Therefore it is difficult to extrapolate the necessary sample size to observe a significant effect using a parallel design and the VitalSense in a patient population. In the first year, we will include 80 patients (40/40 for airweave® and Tempur-Pedic® toppers) and use that data to calculate the sample size needed in order to see statistical effects. We will actively recruit patients with insomnia, since roughly 80% of patients who visit clinic are seen for sleep apnea, and since some insomnia patients may have temperature dysregulation which may partially contribute to their sleep symptoms. An interim analysis will be performed at the end of year 1, once we have studied 40 cases in both arms.

Depending on what is seen in the subgroup of patients with insomnia complaints (we expect the effect to be bigger, especially for those with difficulties with falling sleep, and more clinically meaningful), we will discuss whether it would make sense to focus the rest of the study on patients that have complaints of insomnia.

Years 2-4:

We will include 80/80 patients each year. Year 2 we expect to reach a total of ~ 240 patients, year 3 we will have ~400 and we should have ~ 560 patients in both arms at the end of year 4.

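### The core body temperature ANOVA has no rule for missing telemetry and, on its most natural reading, deletes any patient who lacks one time level; a linear mixed model would keep the readings that exist

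*SAP*

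**What the plan says.** The SAP gives temperature one sentence: "Topper effects on Core body temperature (CBT) was analyzed using two-way mixed method ANOVA with time and topper type as effects". Its opening line says that "SPSS Statistics for Macintosh, version 26 (IBM corp, Armonk, NY) was used for all analysis", and the 0.05 level applies throughout. It does not name the SPSS procedure, the number or width of the temperature time levels, a covariance structure, a random effect, the minimum data needed for a level to count, or what happens when telemetry is missing.

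EEG delta power is handled differently. It has a separate t-test "for each 90 min time bin from lights off", with four bins ending at 360 minutes.

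In the protocol (Materials & Methods), the capsule "will wirelessly send temperature data continuously to the receiver placed in the recording room", and "Patient will have the option to use the capsule as a suppository if they prefer". Sleep and sleep-related symptoms are to be analysed "in segments (e.g. hourly or every 2-hours") as well as over the whole night; the reason given is that the temperature effect appears early in sleep. On design, "the proposed study will use a parallel randomized design in a larger sample". Neither document mentions receiver range, signal loss or an expected rate of missing readings.

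**The concern.** A two-way ANOVA with one within-patient factor (time) and one between-patient factor (topper) is the classical split-plot analysis. In SPSS this is normally run as GLM Repeated Measures, which works on complete records. A patient with no value at one level contributes nothing at any level.

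Lost signal, an expelled capsule, or a night that ends before the last level would each leave such a gap. A gap late in the night would then discard complete data from its first hours. The protocol's background calls the early temperature drop the major finding in healthy volunteers, so these are the readings the trial most needs.

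The bin-by-bin EEG tests do not have this problem: a patient with a short night stays in the early bins. Temperature and EEG results could therefore rest on different patients, although the protocol explains the deeper sleep by the temperature drop.

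Two things are at stake. One is precision. The other, under specific conditions, is the fairness of the randomised comparison.

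**Working it through.** **The plan's own figure.** Enrolment is 80 in year 1 and 160 in each of years 2 to 4: 80 + 3 × 160 = 560, as the protocol states. This is a recruitment target. The documents contain no power calculation or loss rate for temperature to reproduce.

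**Patients kept under complete-record deletion.** Let *k* be the number of time levels and *q* the chance that a level is missing. Both are assumptions. If losses are independent, the share kept is (1 − q)^k.

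- *k* = 4 matches the SAP's EEG bins (360/90), or 2-hour segments over an assumed 8-hour night.
- *k* = 6 or 8 matches hourly segments over 6 or 8 hours.

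| Levels *k* | *q* = 2% | *q* = 5% |
|---|---|---|
| 4 | 0.98^4 = 92% (517 of 560) | 0.95^4 = 81% (456) |
| 6 | 0.98^6 = 89% (496) | 0.95^6 = 74% (412) |
| 8 | 0.98^8 = 85% (476) | 0.95^8 = 66% (372) |

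Many narrow levels would be worse (0.98^32 = 52%), but nothing in the documents points to so many, and adjacent short levels would not be lost independently. If gaps clustered completely, so that a patient had either every level or none, the share kept would be 1 − q, or 95% to 98%. Those lost would then have no readings for any model to use.

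**Precision.** For a simple comparison of two arm means (two-sided 0.05, 80% power), the smallest detectable standardised difference is (1.96 + 0.84) × √(2/n).

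| Share complete | 280 per arm | 40 per arm (year 1 interim) |
|---|---|---|
| 100% | 0.237 | 0.626 |
| 80% | 0.265 | 0.700 |
| 50% | 0.335 | 0.886 |

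**Bias.** A simulation used 280 patients per arm, 6 levels and 1,000 runs per setting. It had a latent poor-sleep score, a topper effect of −0.3, and a chance of missing each level that rose with poor sleep (logistic, intercept −4, slope 1 per SD). About 2% to 3% of levels were missing and 13% to 15% of patients were deleted. Every setting is assumed.

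| Scenario | All data | Complete records | Attenuation |
|---|---|---|---|
| Constant effect, topper does not change sleep | −0.296 | −0.296 | none |
| Topper improves sleep (0.3 SD) | −0.448 | −0.434 | 3% |
| Effect larger in poor sleepers (0.15 per SD) | −0.298 | −0.277 | 7% |
| Both | −0.406 | −0.375 | 8% |

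With a weaker link between poor sleep and gaps (slope 0.5), the last three rows showed about 1%, 4% and 3%. The simulation compares complete records with full data. It does not show how much of the difference a mixed model would recover.

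**The case against.** The SAP's wording does not exclude the SPSS MIXED procedure, which keeps partial records and is the remedy proposed here. That is correct, so the deletion is conditional on the reading. The split-plot vocabulary and the absence of any random effect or covariance structure make GLM Repeated Measures the more natural one. If MIXED was meant, the SAP still needs to say so.

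The time levels are also unknown. If each level averages a continuous signal over one or two hours, a short absence from the room still leaves a value and nobody is deleted. This stands, and it removes brief exits as a major source of loss. It does not cover a capsule expelled early or a night that ends before the last level.

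A reader might infer that restless patients drop out and that temperature is therefore estimated in the better sleepers. The documents do not support this. The capsule transmits whether the patient is awake or asleep, and wakefulness in bed, in the same room as the receiver, creates no gap. Signal faults and expulsion have no stated link to sleep quality. No range or loss rate is given.

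Nor does selection on sleep quality by itself bias the topper contrast, as the constant-effect scenario shows. Bias needs missingness that differs by arm or an effect that varies with sleep quality. The protocol does hypothesise both ingredients: a larger effect in patients with insomnia complaints (Year 1) and better sleep on the airweave topper (Expected results), which could make gaps less frequent in that arm. These are expectations and not evidence of differential loss.

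**Conclusion.** The point holds in a conditional form. The temperature plan is under-specified, and the method it most naturally describes discards valid early-night data from any patient with an incomplete record.

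With 4 to 8 levels and an assumed 2% to 5% independent loss per level, between 8% and 34% of patients would be deleted; clustered gaps would lose fewer. The certain consequence of any such deletion is lost precision. Bias in the topper contrast is possible but modest: up to about 8% attenuation in the scenarios tried, and none when missingness is equal by arm and the effect is constant.

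The documents do not show whether any patient was in fact deleted. They also do not show that the analysed patients slept better than the rest, or that the randomised comparison failed. The point rests on the GLM reading of the SAP and on assumed loss rates. It is a cheap improvement.

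**What to change.** Define the temperature time levels as averages over stated windows from lights off, with a minimum amount of data for a window to count. Replace the ANOVA with a linear mixed model (SPSS MIXED) containing topper, time and topper-by-time and a stated within-patient covariance structure. Use all available readings from every randomised patient who has any temperature data. Report the number contributing at each time point by arm.

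The SAP is dated 2020 and written in the past tense. If the ANOVA has already been run, report the mixed model beside it and label it a re-analysis.

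The cost is a change of SAP wording and a different procedure in the same software, with no new data. There are two downsides. A covariance structure has to be chosen, and after the fact that choice cannot be called pre-specified. The model also still assumes that missingness is explained by topper, time and the observed temperatures. If gaps depend on awakenings beyond that, it addresses the selection only in part, and patients with no temperature data remain outside it.
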